6.3.1 Efficacy laboratory variables

Previous text:

The laboratory parameters that will be measured to assess efficacy are displayed in Table 6 by visit. The results from baseline and onwards will not be reported to the investigator unless FPG value is above 270 mg/dL (15 mmol/L) from Week 0 (Visit 6) to Week 4 (Visit 8), above 240 mg/dL (13.2 mmol/dL) from Week 4 (Visit 8) to Week 12 (Visit 10) and above 200 mg/dL (11.1 mmol/L) from Week 12 (Visit 10) to Week 24 (Visit 13), except for TC, HDL-C, LDL-C and TG which will be reported.

Revised text:

The laboratory parameters that will be measured to assess efficacy are displayed in Table 6 by visit. The FPG results from baseline and onwards will not be reported to the investigator unless FPG value is above 270 mg/dL (15 mmol/L) from Week 0 (Visit 6) to Week 4 (Visit 8), above 240 mg/dL (13.2 mmol/dL) from Week 4 (Visit 8) to Week 12 (Visit 10) and above 200 mg/dL (11.1 mmol/L) from Week 12 (Visit 10) to Week 24 (Visit 13).

Reason for Amendment:

To correct error

Persons who initiated the Amendment:

Study Delivery Team Leader

Clinical Study Protocol Amendment No 1

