3.1.4.1 Rescue Treatment

Subjects with inadequate glycemic control based on glycemic criteria as outlined in Table 1 can remain in the study and can receive rescue therapy with metformin following Japanese local regulation and treatment guideline. In case of intolerability, contraindication or hypersensitivity to metformin or in case of eGFR < 60 ml/min, glymeperide can be used as rescue therapy. In case of inappropriateness of using both metformin and glymeperide, subjects will be withdrawn from this study. If glycemic control is not improved by the rescue therapy, the investigators can consider the discontinuation of the study after consulting with study delivery physician of AZKK.

During Visit 10 (Week 12) to Visit 13 (Week 24), if the results of FPG at the visit show more than 200 mg/dL twice in a row, the investigator consider to start rescue treatment.

Table 1 Criteria for initiation of rescue therapy during the randomised treatment period

Period	Central Laboratory FPG
From Visit 10 (Week 12) to Visit 13 (Week 24)	FPG >200 mg/dL (twice in a row ^a)

a During Visit 10 to 13, if the results of FPG at the visit show more than 200 mg/dL, the investigators should set up acting visit at some other day in order to recheck the FPG at central laboratory. If the results of FPG show more than 200 mg/dL consecutively at this second visit, the investigators can consider to start rescue treatment.

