5.8.1 Criteria for discontinuation from the study

Subjects may be discontinued from study treatment and assessments at any time. Specific reasons for discontinuing a subject are:

General discontinuation criteria:

1. Voluntary discontinuation by the subject who is at any time free to discontinue his/her participation in the study, without prejudice to further treatment
2. Risk to subjects as judged by the investigator, AstraZeneca and/or Bristol-Myers Squibb
3. Severe non-compliance to protocol as judged by the investigator, AstraZeneca and/or Bristol-Myers Squibb
4. Incorrectly enrolled subjects (See Section 5.3)
5. Subject lost to follow-up defined by inability to reach the subject after 3 documented phone calls, faxes, or emails. All attempts at contact should be documented in the subject’s medical record.
6. AE, ie, any clinical AE, laboratory abnormality or intercurrent illness which, in the opinion of the investigator, indicates that continued participation in the study is not in the best interest of the subject

Study-specific discontinuation criteria:

7. Use of (need for) any anti-diabetic agents, except for rescue treatment, other than investigational product.
8. Treatment with systemic glucocorticoids equivalent to oral prednisolone ≥ 10 mg/day (two temporary periods of higher daily doses for no longer than 7 days each are allowed)
9. Major and/or frequent hypoglycemic events; If more than one event of severe hypoglycemia, defined as symptomatic events requiring external assistance due to severe impairment in consciousness or behaviour, with a capillary or plasma glucose value < 3 mmol/L (< 54 mg/dL), and prompt recovery after glucose or glucagon

administration occurs, or if the investigators decides that current treatment poses the subject at risk of either repeated hypoglycemic events or severe hypoglycemia.

10. Pregnancy confirmed by a positive pregnancy test or otherwise verified
11. Change in kidney function (see Appendix F for further guidance):
 - For subjects treated with metformin: For subjects with a central laboratory eGFR <60 mL/min or with an increase in SCr of ≥ 0.5 mg/dL (44.2 $\mu\text{mol/L}$) above the baseline value (Visit 6), an increase in SCr of ≥ 0.5 mg/dL above the baseline value (Visit 6) confirmed by a repeated measurement within one week or eGFR <60 mL/min
 - For subjects not treated with metformin: Subject with following criteria will be scheduled for an additional visit within one week.
 - (a) eGFR <45 ml/min

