6.3 Efficacy

6.3.1 Efficacy laboratory variables

The laboratory parameters that will be measured to assess efficacy are displayed in [Table 6](#) by visit. The results from baseline and onwards will not be reported to the investigator unless FPG value is above 270 mg/dL (15 mmol/L) from Week 0 (Visit 6) to Week 4 (Visit 8), above 240 mg/dL (13.2 mmol/dL) from Week 4 (Visit 8) to Week 12 (Visit 10) and above 200 mg/dL (11.1 mmol/L) from Week 12 (Visit 10) to Week 24 (Visit 13), except for TC, HDL-C, LDL-C and TG which will be reported.

Table 6 Efficacy laboratory variables

Visit	1	2	3	4	5	6	7	8	9	10	11	12	13	14
Study week	-12 or -6	-10	-7	-4	-1	0	1	4	8	12	16	20	24	27
HbA1c	X				X	X		X	X	X	X	X	X	X
FPG	X	X	X	X	X	X	X	X	X	X	X	X	X	X
Insulin	X					X			X		X		X	
C-peptide	X					X			X		X		X	
Glycoalbumin	X					X		X	X	X	X	X	X	

Table 6 Efficacy laboratory variables

Visit	1	2	3	4	5	6	7	8	9	10	11	12	13	14
Study week	-12 or -6	-10	-7	-4	-1	0	1	4	8	12	16	20	24	27
TC						X								X
LDL-C						X								X
HDL-C						X								X
TG						X								X
FFA						X								X

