6.4.9.1 Fasting plasma glucose concentrations and hypoglycemic events

Subject self-monitoring of FPG is performed in order to reduce the risks associated with prolonged hyperglycemia and to confirm symptoms of hypoglycemia. Subjects will be asked to perform self-monitoring of FPG using glucometers provided by AstraZeneca. The subjects will receive instructions for the use of the glucometer according to the manufacturer's instructions.

FPG should be self-monitored at least every second day between Visits 2 and 6 and at least once a week between Visits 6 and 8. The results should be recorded in the subject diary, which will be

collected and reviewed by the study personnel at each visit starting with Visit 3; a print out will be stored in the investigator study file.

The memory of the glucometer should be reviewed and compared with the readings in the subject's diary. The glucose values should be reviewed by the study personnel to identify any unusually high or low values, and to confirm that self-monitoring was performed by the subject. If fingerstick glucose values are discordant with central laboratory results or with clinical symptoms, the subject's glucometer should be tested and the glucometer instructions should be re-reviewed with the subject.

If self-monitored FPG is above 270 mg/dL (15 mmol/L) from Week - 4 (Visit 4) to Week 4 (Visit 8), and above 240 mg/dL (13.2 mmol/L) from Week 4 (Visit 8) to Week 24 (Visit 13), the subject should repeat the FPG on the same day. If the second FPG value is above 270 mg/dL (15 mmol/L), or 240 mg/dL (13.2 mmol/L), respectively, the subject should contact the study centre and be scheduled for a central laboratory FPG measurement within one week.

If central laboratory values show similar values, the subject should be discontinued.

A separate section in the eCRF will be used to document all reported episodes of hypoglycemia after Week - 4 (Visit 4). The subjects will be asked to check their blood glucose if they develop symptoms suggestive of hypoglycemia and to record specific symptoms in the subject diary. The Investigator is responsible for questioning the subject about all symptoms reported in the diary and for determining if they meet the clinical definition of hypoglycemia. Only symptoms and/or blood glucose values that meet the definition of hypoglycemia should be reported on the hypoglycemia eCRF pages.

A hypoglycemic event can be either:

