- Symptoms of hypoglycemia with a low blood glucose reading (<63 mg/dL [<3.5 mmol/L])
- A low blood glucose reading (<63 mg/dL [<3.5 mmol/L])
- Symptoms of hypoglycemia without a blood glucose reading

Hypoglycemic episodes or discontinuation due to hypoglycemia should not be reported on the AE eCRF page unless the event fulfils protocol criteria for a SAE (See Section 6.4.2). In this case, an SAE must be reported in addition to the hypoglycemia eCRF pages for hypoglycemia.

Symptoms suggestive of hypoglycemia with an associated capillary or plasma glucose value ≥ 63 mg/dL (≥ 3.5 mmol/L), should be recorded as an AE rather than as a hypoglycemic event. If the physician does not consider the glucose measurement to be accurate, however, the event should be documented as a hypoglycemic event in the hypoglycemia eCRF.

For the evaluation of hypoglycemic events, this study will use the definitions provided in the CPMP guidance on clinical investigation of medicinal products in the treatment of diabetes mellitus, as described below.

- Major hypoglycemic events, defined as symptomatic events requiring external assistance due to severe impairment in consciousness or behaviour, with a capillary or plasma glucose value <54 mg/dL (<3.0 mmol/L), and prompt recovery after glucose or glucagon administration.
- Minor hypoglycemic event, defined as either a symptomatic episode with a capillary or plasma glucose measurement <63 mg/dL (<3.5 mmol/L) regardless of need for external assistance or an asymptomatic capillary or plasma glucose measurement below 63 mg/dL (3.5 mmol/L) , that does not qualify as a major episode
- Events suggestive of hypoglycemia, defined as a symptomatic event without a confirmatory blood glucose measurement.

Data to be collected for each hypoglycemic event:

- Date and time of episode (start and stop)
- Whether the subject was sleeping at the time of the event
- Whether symptoms were present, and list of symptoms
- Possible contributing factors
- Whether a fingerstick value was obtained, and if so, the plasma glucose value
- Whether intervention was needed for recovery
- How the episode was treated
- Whether recovery was prompt after treatment
- Time of last anti-diabetic agents administration
- Time of last meal and its contents

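### Amended Section 6.3.1 releases central FPG to the investigator only when it is high, so a markedly low asymptomatic value has no stated route to the site during treatment (minor subject-safety point)

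*Protocol*

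**What the plan says.** **Release rule.** The revised Section 6.3.1 (Amendment No 1) reads "The FPG results from baseline and onwards will not be reported to the investigator unless FPG value is above 270 mg/dL" for Week 0 to Week 4. It then uses 240 mg/dL to Week 12 and 200 mg/dL to Week 24. Section 6.3.1 in the body of the protocol has the same limits in a broader sentence, "The results from baseline and onwards will not be reported to the investigator unless FPG value is above 270 mg/dL". The amendment narrowed the withholding to FPG and left the limits as they were.

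**Low glucose as a safety event.** Section 6.4.9.1 counts "an asymptomatic capillary or plasma glucose measurement below 63 mg/dL (3.5 mmol/L" as a minor hypoglycemic event when it does not qualify as major. The glucose limit in the major-event definition is 54 mg/dL. One limb of discontinuation criterion 9 (Section 5.8.1) is the investigator's judgement that "current treatment poses the subject at risk of either repeated hypoglycemic events or severe hypoglycemia".

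**Other routes for glucose data.** Section 6.4.9.1 asks for home testing "at least every second day between Visits 2 and 6 and at least once a week between Visits 6 and 8". After Visit 8 it gives no minimum frequency, but subjects are asked to test when they have symptoms. Table 2 keeps meter and diary instruction going to Visit 13 and hypoglycemia assessment to Visit 14. Table 7, the safety laboratory panel, has no plasma glucose.

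**Rescue.** From Week 12, Section 3.1.4.1 allows metformin rescue. For intolerance, contraindication or hypersensitivity to metformin, "or in case of eGFR < 60 ml/min, glymeperide can be used as rescue therapy".

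**The concern.** The rule is exclusive (not reported unless high) and works in one direction only. A central FPG below 54 mg/dL meets no release condition at any treatment visit. If the subject has no symptoms and has not tested at home that day, nothing in the protocol brings the value to the site.

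The investigator then cannot contact the subject, cannot consider whether the value is a minor event, and cannot weigh it under criterion 9. The matter is one of subject safety during conduct. A statistical analysis plan cannot repair it, because it does not decide who sees a result while the trial is running. A laboratory manual, which is not shown, might contain a low alert, but such an alert would run against the protocol sentence as written.

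**Working it through.** No figure in the plan is in dispute, so the check sets the sections side by side and counts the samples under the rule.

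**Inputs**
- Randomised subjects: 85 per arm, 255 in total (Section 12.3). This reproduces: 80 / 0.95 = 84.2, rounded up to 85, and 3 × 85 = 255.
- FPG schedule (Tables 2 and 6): Visits 6 to 13 at Weeks 0, 1, 4, 8, 12, 16, 20 and 24.
- Last stated home-testing minimum: Visit 8, Week 4 (Section 6.4.9.1).
- Earliest rescue: on the Week 12 result, after a confirming repeat (Table 1).
- Visit 6 is the pre-dose baseline (Section 11.1.1), so it is left out of the treatment count although the rule covers it.

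**Does any low value meet a release condition?** The three conditions are FPG above 270, 240 and 200 mg/dL. Values below 63 or 54 mg/dL meet none of them at any visit.

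**Is there another stated route for an asymptomatic low?**

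| Route | Reaches the site? |
|---|---|
| Symptom-prompted meter test | Not without symptoms |
| Scheduled home test | Minimum frequency stated to Week 4 only |
| Safety panel (Table 7) | No plasma glucose |
| HbA1c, glycoalbumin | No longer withheld after the amendment, but they reflect average glycemia and do not show a single low value |
| Sponsor review (Sections 1.4 and 11.2.2) | General and by judgement; neither section says that a low FPG goes back to the site |

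**Samples under the rule** (upper limits, ignoring dropout)
- Visits 7 to 13: 7 per subject; 7 × 85 = 595 per arm; 7 × 255 = 1785 in total.
- Visits 9 to 13: 5 per subject; 5 × 85 = 425 per arm; 5 × 255 = 1275 in total.
- Treatment weeks with no stated home-testing minimum: (24 − 4) / 24 = 83%.
- Scheduled samples that can follow rescue started on the Week 12 result: at most 3 per rescued subject (Weeks 16, 20 and 24).
- Study drug stops at Visit 13 (Section 3.1.5), so the Week 24 value could prompt contact but could no longer inform a decision to stop treatment.

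The document gives no FPG distribution, so these counts cannot be turned into an expected number of low values.

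**The case against.** **No contradiction.** A reader might infer that Section 6.4.9.1 requires site staff to look at central lows, because it says "The glucose values should be reviewed by the study personnel to identify any unusually high or low values". The documents do not support that. The sentence directly follows the instruction to compare meter memory with the diary, so it concerns meter and diary readings. The reference to plasma glucose in the minor-event definition is also not decisive. Section 6.4.9 calls the meter readings plasma glucose, and event data are transcribed from the diary. The definition can cover a central sample but does not clearly demand it. This objection stands: the point is a gap, not an inconsistency.

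**Monitoring continues.** Meters, diaries and hypoglycemia assessment run through Visit 13, and Section 6.4.9.1 sets high-glucose action limits for home tests up to Week 24. Only the minimum frequency lapses. This also stands and limits the size of the point.

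**The route to harm is thin.** An isolated low laboratory value cannot be a major event, because that needs symptoms and external assistance. A single minor event requires no contact from the subject. Rescue needs FPG above 200 mg/dL twice in a row, and glimepiride is second line. It would therefore go too far to infer that subjects on glimepiride are left unmonitored or that lows in that group are likely. Nothing in the document shows either.

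**Blinding.** Withholding FPG is a reasonable blinding measure, and a low alert adds a cue. But the protocol already accepts a cue of this kind for high values, and low alerts should be rare.

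None of these objections supplies a stated route by which an asymptomatic low central FPG reaches the investigator.

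**Conclusion.** The point holds as a minor subject-safety gap. As written, Section 6.3.1 withholds a markedly low central FPG at all seven post-baseline treatment visits, and five of these fall after the last stated home-testing minimum.

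The conclusion rests on reading the release sentence literally and on there being no low-value alert elsewhere in the protocol. The number of values affected is unknown and probably very small: entry requires HbA1c of at least 6.5% at Visit 5, and treatment is monotherapy unless the subject is rescued.

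A reader might also infer that hypoglycemia would be under-counted differently between arms, or that efficacy results are at risk. The documents support neither. The rule is the same in all arms, and the HbA1c, FPG and weight analyses do not depend on what the site is shown.

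**What to change.** Add one sentence to Section 6.3.1: central FPG below 54 mg/dL at any visit from Week 0 is also reported to the investigator. This is the protocol's own glucose limit for a major event. It keeps alerts rarer than a 63 mg/dL limit would, and it covers rescued subjects without a separate rule.

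The cost is one amendment sentence and one central-laboratory alert. The downside is a rare extra unblinding cue, similar in kind to the existing high-value release. Sample size, significance levels and analyses do not change.
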